2.3.2. Risks of use of Investigation product: Prolastin-C

Because clinical studies for Prolastin-C are conducted under widely varying conditions, adverse reaction rates observed cannot be directly compared to rates in other clinical trials and may not reflect the rates observed in practice. According to the Prolastin-C package insert, the most serious adverse reaction observed during clinical studies with Prolastin-C was an abdominal and extremity rash in one subject. The rash resolved subsequent to outpatient treatment with antihistamines and steroids. Two instances of a less severe, pruritic abdominal rash were observed upon re-challenge despite continued antihistamine and steroid treatment, which led to withdrawal of the subject from the trial.

The most common drug-related adverse reactions observed at a rate of $> 1\%$ in subjects receiving Prolastin-C were chills, malaise, headache, rash, hot flush and pruritus. Adverse reactions considered drug related by the investigators occurring in 1.6% of subjects (one subject each) treated with Prolastin-C were malaise, headache, rash, hot flush, and pruritus. Drug related chills occurred in 3.2% (2 subjects) of Prolastin-C subjects.

Products made from human plasma may carry a risk of transmitting infectious agents, e.g., viruses, and, theoretically, the Creutzfeldt-Jakob disease (CJD) agent. In each of 2 randomized, double-blind studies in which the predecessor product, PROLASTIN® (Alpha1-Proteinase Inhibitor [Human]), was compared to other AAT products, there was a single case of parvovirus

B19 seroconversion in the Prolastin-C arms of each trial. In each case, it could not be determined whether parvovirus had been acquired from Prolastin-C or from the community. However, during clinical studies with Prolastin-C, there were no reported treatment emergent cases of hepatitis B, hepatitis C, HIV or parvovirus B19 viral infections. Furthermore, the Prolastin-C process incorporates additional plasma safety and virus reduction measures that minimize the residual risk of virus transmission. Risk for placebo: patient may not be receiving a therapy as good as the alternative arm of the study. There is no other risk to placebo infusion at the dose provided.

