2.4.2. Benefits to society

This study may identify a useful medication that will benefit patients with islet transplantation.

3. OVERALL STUDY DESIGN AND PLAN DESCRIPTION:

3.1. STUDY DESIGN:

Experimental design: We propose to enroll a total of 48 CP patients who are scheduled for TP-IAT. This will be a 2:1 randomized, double blind, controlled study in which 32 patients receive islet cell transplantation together with intravenous AAT 60 mg/kg/week for 4 weeks, and 16 patients receive islets with intravenous 0.9% saline control in equivalent volume.

CP patients planning TP-IAT will receive an IRB approved consent form that describes the research study. Following signed consent, they will be enrolled and receive a baseline study visit. On the day of TP-IAT, an intravenous injection of AAT at the FDA approved dose of 60mg/kg or 0.9% normal saline will be infused before surgery. The autologous islet transplantation procedures will remain as routinely performed at MUSC. On the day of transplantation, the pancreas will be harvested and transferred to the Center for Cellular Therapy (CCT). Islets will be isolated and transplanted back to the patient via portal vein infusion. AAT or placebo will be given on day 0, 7, 14 and 21 days of islet transplantation.

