6.1. HOSPITAL STAY

6.1.1. Patient recruitment, blinding and randomization

Subjects will be recruited from the clinical offices of Drs. [name] and [name] during their routine preoperative evaluation for pancreas resection and islet transplantation. During their preoperative evaluation, the purpose of the study and the associated consent form will be explained in detail and the participant will be given time to ask questions. If the subject wishes to participate, the proper consent and HIPAA forms will be signed and dated. The consent form may be signed in person in a clinic or via telehealth using an eConsent/doxy.me. On the doxy.me platform the study participant has the ability to download a copy of the signed consent for their record. They will be informed of this and encouraged to download their copy by the study team member who is obtaining consent. The virtual visit video chat feature of this platform allows for questions from the patient to be answered in real time by the study team. The study team member obtaining consent will also have the ability to review the HIPAA authorization form with the patient and obtain a signature through the doxy.me platform. A copy of the signed consent form will accompany the patient to the operating room for documentation of participation in the study.

Consented patients will be screened based on inclusion and exclusion criteria. If patient meets the criteria, they will be randomized to either AAT or control group by block randomization. The PI ([name]) and the clinical PIs ([name], [name], [name], [name]) of this study will be blinded for the assignment of the study treatment. The Investigational Pharmacy at MUSC will prepare drug infusions using aseptic technique under a sterile hood. In the clinic, a trained RN will infuse the drug and monitor for side effects of AAT. These individuals will not be blinded.

Diabetes care will be managed by the Endocrinology team at MUSC led by [name], co-investigator of our trial. The diabetes care is standardized while in the hospital with insulin drip for all patients post-operatively. The drip is then weaned over the first few days with care individualized by the hospital diabetes management team. The discharge plan is then individualized in accordance with ADA standards.

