6.1.2 Infusion of the Investigational Product

Infusion of AAT will start on the day of islet transplantation before anesthesia and pancreatectomy, which is approximately 6-8 hours before islet infusion. The clinical PIs, Drs. [name] and [name], will identify the time to start the study drug infusion. Starting and ending time of drug administration, amount of drug infused, and infusion rate will be recorded for each subject. On Average, TP-IAT patients stay in the hospital for 7-28 days after islet transplantation. If they stay till 21 days post transplantation, they can have all four AAT injections in the hospital. If they are discharged earlier, patients will be requested to return to MUSC for additional drug infusion(s). A nurse will administer the AAT or placebo infusion to the patient while in the hospital. A nurse in the GI surgery clinic or SCTR outpatient clinic will administer AAT or placebo to patients discharged but returning for one of the weekly visits. The nurses infusing these drugs will be trained on the day of administration concerning the few known side effects of AAT and rate of infusion.

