8.3. SAMPLE SIZE JUSTIFICATION

We recognize that the number of participants is small given the heterogeneity of chronic pancreatitis but believe the numbers are appropriate for a proof-of-concept translational study. The goal of this aim would be to test whether IAT + AAT is feasible in this patient population and to obtain preliminary assessments of its success. Having n=32 subjects treated with AAT

(and n=16 placebo controls) would allow us to make relatively precise estimates of feasibility measures and means of the study outcomes, with 95% confidence intervals that would extend approximately 0.3 standard deviation units in either direction. While recognizing that the standard deviation will be slightly higher in the control population, we recognize that all hypothesis testing will be considered exploratory, enabling 80% power to detect moderately large differences (effect sizes of 0.9 standard deviation units) between the AAT and treated control groups with respect to the study outcomes, including the 4 hour C-peptide level AUC obtained at 12 months, assuming up to a 10% loss to follow-up over the 12 months. Having these numbers of subjects would also allow us to make preliminary comparisons between outcomes in the IAT + AAT group and outcomes observed in a group of 150 historical controls, each of whom received a total pancreatectomy with IAT at MUSC from 2009-2015. Most importantly, the data (e.g. means, standard deviations, and effect size estimates) from 32 subjects receiving AAT treatment, 16 control subjects receiving islets alone, and 150 historical controls will be vital for use in designing a larger more definitive randomized controlled trial in the future. Using 2:1 randomization will help provide more precise estimates of outcomes in the IAT + ATT group and may also help with study recruitment, as subjects may tend to be more willing to consent if they have a stronger probability of receiving the active experimental treatment.

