8.10. SAFETY ANALYSES

Study subjects will be asked to report any and all AEs/new symptoms at any time from study enrollment until 52 weeks after study treatment, whether or not they attribute them to the study intervention or procedures. Subjects, who discontinue the study treatment regimen for any reason, including subjects who are treatment failures due to unable to return for some of the treatment injection(s) will be encouraged to attend the remaining visits for assessment of safety, secondary and pharmacokinetic endpoints.

To assess safety in this population, vital signs will be performed at each of the study visits. Additionally, medical history will be collected at screening and baseline and adverse events occurring after start of study therapy will be recorded.

Since the safety endpoints are primarily binary indicators for each subject (e.g. experiencing a particular AE during the 24-weeks post-treatment), their analyses will involve logistic regression models. For certain safety endpoints, it may be more appropriate for them to be analyzed using survival techniques, which are more suitable for time-to-event data than logistic regression. In such circumstances, Cox proportional hazards models will be used to compare treatment arms; however, should the proportionality assumptions not hold, alternative strategies (e.g. stratified analyses) will be used. The safety analyses will be conducted in the Safety Population.

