8.11. SECONDARY EFFICACY ANALYSIS

A series of secondary efficacy and exploratory endpoints will be evaluated, as listed in Section 3.5.2 and 3.5.3. All secondary analyses will be conducted in an exploratory fashion with p-values and confidence intervals presented with no adjustments for multiple comparisons. Interval estimates will be generated at the 95% confidence level. Secondary analyses will be conducted on the mITT population and the per protocol population. Since most secondary endpoints will be collected at multiple time points for each participant, generalized linear mixed models will be utilized, as they are appropriate for longitudinal data analyses and can be adapted for binary dependent variables.

Secondary endpoints analyses are used to confirm or support the findings based on the primary outcome analysis. If most of the secondary endpoints show a change in the opposite direction

from the primary efficacy analysis or no direction, we might have less confidence in the primary endpoint.

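### Section 8.10 plans no adverse event analysis timed to the infusions, so an excess of the listed drug reactions is diluted by months of post-surgical background

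*Combined protocol and SAP*

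**What the plan says.** Section 8.10 describes the safety endpoints as primarily binary per subject, gives as its example "experiencing a particular AE during the 24-weeks post-treatment", and analyses them by logistic regression. Cox models are allowed for certain endpoints. Neither method is given a window defined by the infusions, and no endpoint in Section 3.5.4 has one.

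Section 2.3.2 gives the most common drug-related reactions in subjects on "Prolastin-C were chills, malaise, headache, rash, hot flush and pruritus". The cited rates are 3.2% for chills and 1.6% for each of the others. The same section names transmission of infectious agents as a further risk and gives no onset times for the listed reactions.

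Infusion-time information is collected:

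- Section 6.1.2: "Starting and ending time of drug administration, amount of drug infused, and infusion rate will be recorded for each subject".
- Section 6.1.1: "a trained RN will infuse the drug and monitor for side effects of AAT". It adds that these staff are not blinded.
- Section 5.2: vital signs before, during and 15 minutes after each infusion.
- Appendix 1: adverse events recorded at every dosing visit.

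None of this is carried into Section 8.10.

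**The concern.** The objective in Section 3.4 includes comparing safety. After total pancreatectomy, several of the listed reactions are likely to occur in both arms for reasons unrelated to the drug; Section 2.3.1 accepts that all these patients are at risk of complications whether or not they join the study. A subject who has had any headache in the period already scores yes, so a headache caused by an infusion adds nothing to the indicator. The arm comparison then understates an infusion-related excess, most of all for non-specific symptoms. At stake is whether the trial can hand a usable infusion-reaction rate by arm to the larger trial that Section 8.3 says it is meant to inform.

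**Working it through.** **The plan's own figure.** There is none for safety. Section 8.3 gives an efficacy figure: "enabling 80% power to detect moderately large differences (effect sizes of 0.9 standard deviation units" with 32 against 16, "assuming up to a 10% loss to follow-up over the 12 months". With 28.8 against 14.4 remaining, SE = √(1/28.8 + 1/14.4) = 0.323 and power = Φ(0.9/0.323 − 1.96) = 79.6%. It reproduces but says nothing about adverse events.

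**Inputs**

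- 32 on AAT, 16 on placebo (Section 3.1).
- Drug-related rates of 1.6% and 3.2% (Section 2.3.2).
- Two-sided 0.05: assumed, since no test level is stated. Section 8.11 uses 95% intervals.
- Background b: not in the documents. Assumed 40–80% over 24 weeks and 2–10% over the four infusion windows, with 20–30% as a stress case.
- Infusion-caused share q: the cited rates, and larger assumed values.

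**Step 1: dilution.** If background and infusion-caused events are independent, the AAT rate is 1 − (1 − b)(1 − q), so the arm difference is q(1 − b). For chills at q = 3.2%:

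- b = 40%: 3.2 × 0.60 = 1.9 points
- b = 80%: 3.2 × 0.20 = 0.6 points
- b = 2%: 3.2 × 0.98 = 3.1 points
- b = 10%: 3.2 × 0.90 = 2.9 points

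**Step 2: why window background is lower.** Four 24-hour windows are 4 of 168 days, or 2.4%. At a constant hazard, 24-week backgrounds of 40, 60 and 80% become 1 − (1 − B)^(4/168) = 1.2, 2.2 and 3.8%. Post-surgical symptoms cluster early, so the true figure is probably higher. That is the reason for the 2–10% range and the stress case.

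**Step 3: precision at q = 3.2%.** Half-width = 1.96 × √[p(1 − p)/32 + b(1 − b)/16], with p the AAT rate (normal approximation):

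- b = 2%, p = 5.1%: 10 points
- b = 10%, p = 12.9%: 19 points
- b = 20–30%: 24–28 points
- b = 50%, p = 51.6%: 30 points
- b = 80%: 24 points, but with only 0.6 points of excess left to see

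**Step 4: power.** Fisher exact test by enumeration, 32 against 16, counting rejections toward AAT harm:

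| q | Ever in 24 weeks, b = 40/50/60/80% | Windows, b = 2/5/10% | Windows, b = 20/30% |
|---|---|---|---|
| 3.2% | 2/2/2/2% | <1/<1/1% | 2/2% |
| 10% | 4/3/3/3% | 2/4/6% | 5/4% |
| 20% | 8/7/6/4% | 30/27/22% | 14/10% |
| 30% | 16/12/10/7% | 71/60/45% | 28/21% |

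For 80% power, q must be about 39% at b = 5% and about 71% at b = 40%.

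**Step 5: what description can give.** Among 32 on AAT, the chance of at least one drug-related chill at 3.2% is 1 − 0.968³² = 65% (1.0 expected). At 1.6% it is 1 − 0.984³² = 40% (0.5 expected). No events in 32 gives an exact upper 95% limit of 1 − 0.025^(1/32) = 10.9%; none in 16 gives 1 − 0.025^(1/16) = 20.6%.

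**The case against.** - **Section 8.10 is not exclusive.** It says primarily, offers the 24-week indicator as an example and allows Cox models. A reader might infer that every adverse event is scored ever/never; the text does not say so. What stands is that no infusion-timed analysis is written anywhere.
- **Reactions are not invisible.** Section 7.1.1 has the investigator assess severity and relationship to treatment, Section 8.1 puts relatedness in the reports by group A and B, and the DSMB reviews all events. A reader might infer that reactions would go unseen; these listings may show individual cases. They rest on attribution, though. Section 7.1.3 defines relatedness categories for serious events only, and Section 7.2 says no events are expected from the infusions, which sits badly with Section 2.3.2.
- **Not all named harms are shown to be acute.** Infection transmission needs long follow-up, and no onset times are given. This is a reason to keep the long-window analysis.
- **Dilution is uneven.** The documents give no reason to expect a high background of rash, hot flush or pruritus. For these, ever/never scoring may lose little.
- **The window is not clean.** The day-0 window contains the operation, and with stays of 7–28 days (Section 6.1.2) later doses can fall in early recovery. This is why the stress case is shown.
- **Unblinded observers.** Subjective symptoms noted by staff who know the assignment are open to ascertainment bias. This stands, and it rules out presenting the windowed comparison as a formal test.

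**Conclusion.** The point holds as a gap in the analysis plan. Data are gathered around each infusion, but Section 8.10 plans nothing timed to the infusions, and its main form of comparison keeps only a fraction (1 − b) of any infusion-caused excess. That is 20–60% at assumed 24-week backgrounds of 40–80%, against 90–98% at assumed window backgrounds of 2–10%.

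A reader might take the 71% against 12% contrast in the power table as the size of the gain. The documents do not support that: it needs a causal rate of 30%, which is 30/3.2 = 9 to 30/1.6 = 19 times the cited rates, and the 71% falls to 21–28% if window background is 20–30%. At the cited rates power is about 2% or less either way. Section 8.3 also declares all hypothesis testing exploratory, so power is a weak yardstick here. What is gained is a more precise and interpretable rate by arm, and a chance of detecting a large excess. Every background rate is an assumption, and so is onset of these reactions within 24 hours.

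**What to change.** Keep the whole-follow-up adverse event analysis in Section 8.10, which is also needed for later harms such as infection transmission. Add one descriptive table by arm:

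- **Events:** the reactions listed in Section 2.3.2 that start between the start of an infusion and 24 h after its end.
- **Units:** subjects with at least one such event, and infusions followed by one, over those actually infused. The Safety Population in 8.2.3 does not require an infusion.
- **Presentation:** exact 95% intervals and investigator relatedness. For infusions, note that a subject's four infusions are not independent, so that interval is approximate.
- **Layout:** day 0 separate from days 7, 14 and 21.
- **Footnote:** infusing and monitoring staff are not blinded (6.1.1), so the table is descriptive and not a formal test.

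The cost is a paragraph of SAP text, one table and possibly a change to the case report form. Infusion times are already recorded, but the documents do not say that onset time of adverse events is. On infusion days it must be recorded at least as same or next day. While this section is open, the 24-week example should be reconciled with the 52-week reporting period stated in the same section.

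### Section 8.10 plans logistic or Cox regression for adverse events in arms of 32 and 16; for uncommon events this will often give no finite estimate, and no sparse-data method is named

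*Combined protocol and SAP*

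**What the plan says.** Section 3.1 sets 2:1 allocation: "32 patients receive islet cell transplantation together with intravenous AAT 60 mg/kg/week for 4 weeks"; the saline placebo arm has 16. Section 8.10 describes the safety endpoints as mainly one yes/no indicator per subject for a given AE and says "their analyses will involve logistic regression models". Where time to event suits better, "Cox proportional hazards models will be used to compare treatment arms". The only contingency is that "should the proportionality assumptions not hold, alternative strategies (e.g. stratified analyses) will be used".

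The section names no estimation method, type of interval or test, minimum event count, or procedure for an arm with no events. Section 8.9, by contrast, gives the efficacy analysis transformations and non-parametric alternatives if model assumptions fail.

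The only AE rates in the document are in Section 2.3.2, from earlier studies of the product. Several drug-related reactions each occurred in 1.6% of subjects, and "Drug related chills occurred in 3.2% (2 subjects) of Prolastin-C subjects". Section 7.2 expects no events from either infusion.

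**The concern.** Comparing safety is part of the study objective (Section 3.4), and AE incidence is the first safety endpoint in Section 3.5.4. With 16 controls, an uncommon AE can easily be absent from one arm. The likelihood then has no interior maximum: the fitted log odds ratio drifts towards plus or minus infinity, and its standard error becomes very large. A Cox model does not help, because its partial likelihood is also monotone when one arm has no events.

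What is at stake is a usable estimate and interval for uncommon events. Section 8.3 says the trial's effect estimates are meant to inform a larger trial, and an infinite odds ratio with a default p-value near 1 cannot do that.

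**Working it through.** **Inputs.** Arms of 32 and 16 (Section 3.1). Rates of 1.6% and 3.2% (Section 2.3.2). The document gives no background AE rate for this surgery, so rates of 5% and above are assumptions. It also gives no power or precision figure for safety, so there is no planned figure to reproduce. The safety population (Section 8.2.3) is taken as 32 + 16.

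**How often the odds ratio is not finite.** For a true rate p in both arms, P(no events in an arm of n) = (1 − p)^n. At low rates, P(no finite odds ratio) = 1 − [1 − (1 − p)^16][1 − (1 − p)^32], which includes the case where both arms are empty. At p = 5%: 0.95^16 = 0.440 and 0.95^32 = 0.194, so 1 − 0.560 × 0.806 = 0.549.

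| True rate, both arms | P(0 of 16) | P(0 of 32) | P(no finite odds ratio) | P(exactly one arm empty, given at least one event) |
|---|---|---|---|---|
| 1.6% | 77.3% | 59.7% | 91% | 83% |
| 3.2% | 59.4% | 35.3% | 74% | 67% |
| 5% (assumed) | 44.0% | 19.4% | 55% | 51% |
| 10% (assumed) | 18.5% | 3.4% | 21% | 21% |
| 15% (assumed) | 7.4% | 0.6% | 7.9% | 7.9% |
| 20% (assumed) | 2.8% | 0.1% | 2.9% | 2.9% |
| 30% (assumed) | 0.3% | 0.0% | 0.3% | 0.3% |

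If the rates differ, for example 5% on placebo and 20% on AAT, the chance is 44%. The problem returns at very high rates, when everyone in an arm has the event: 21% at 90% and 55% at 95%.

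**What the output looks like.** Take 10/32 on AAT and 0/16 on placebo.

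- Unpenalised logistic regression stopped at 25 iterations: log odds ratio about 21.8, standard error about 12,049, Wald p = 0.999.
- Fisher's exact test: with 10 events in all, P(0 on placebo) = C(32,10)/C(48,10) = 0.0099. The tables with 7 or more placebo events are less probable than this and add 0.0097. Two-sided p = 0.020.
- Risk difference: 10/32 − 0/16 = 31.3 points. The Wilson limits are 18.0% to 48.6% for 10/32 and 0% to 19.4% for 0/16. Newcombe lower limit: 0.3125 − √[(0.3125 − 0.180)² + 0.194²] = 0.078. Upper limit: 0.486. The 95% interval is about 8 to 49 points.
- Likelihood-ratio test from the same unpenalised model: p = 0.002.
- Firth estimate, which for a 2×2 table amounts to adding 0.5 to each cell: (10.5 × 16.5)/(22.5 × 0.5) = 15.4. Its Wald-type 95% interval is 0.84 to 282, so even a penalised fit should be paired with a profile-likelihood interval.

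**The case against.** The strongest reply is that Section 8.10 never commits to Wald inference. Exact, Firth-penalised and likelihood-ratio or profile-likelihood methods are all forms of logistic regression and fit the text. A likelihood-ratio test and a one-sided profile bound survive a zero cell. That stands: the gap is one of specification, and p near 1 applies only to default Wald output. It does not restore a finite unpenalised estimate, and the choice of inference should not wait until the data are seen.

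A reader might infer that the planned model would conceal any one-sided imbalance. The document does not support this. For 5/32 versus 0/16, the likelihood-ratio test from the planned model gives p = 0.037, while Fisher's test gives 0.154. AE incidence is itself an endpoint, so the counts should be seen. Under Section 8.5 the DSMB may also unblind fully at any time.

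A reader might also infer that the whole safety comparison fails. It does not. The 1.6% and 3.2% rates are drug-related reactions in another setting, whereas this trial collects all AEs for 52 weeks after major surgery, and many of those may be common. AEs at roughly 15% to 85% are largely unaffected. So are the laboratory, vital sign, weight and albumin endpoints of Section 3.5.4, which are not rare binary events.

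Finally, Section 8.3 calls all hypothesis testing exploratory, and the stopping rules in Section 5.5 do not use a safety p-value. That limits the consequence, although exploratory work relies on the very estimates and intervals that are lost.

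**Conclusion.** The point holds for uncommon individual AEs, with a true rate of about 10% or less. There the planned regression has no finite odds ratio in at least 21% of cases, rising to 74% at 3.2% and 91% at 1.6%. These figures assume equal rates in both arms, full arms of 32 and 16, and treatment as the only covariate. How many of the trial's AEs fall in this range cannot be determined from the document. The consequence is moderate: safety is part of the objective, but testing is exploratory and counts can still be tabulated. It is worth correcting because a better method is available at almost no cost.

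**What to change.** In Section 8.10, state that each binary safety endpoint will be reported as n/N per arm with the risk difference and a score-based or exact 95% confidence interval, and with Fisher's exact test if a p-value is wanted. Add that any logistic or Cox regression will be Firth-penalised, with profile-likelihood intervals.

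This takes about two sentences and uses standard options in SAS, which Section 8.6 already names. Design, data collection and sample size do not change. The downside is that exact methods are slightly conservative.
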